#### **8.10.5 Progression-Free Survival**

Analyses will be performed on the FAS and at subject level. On run-in set, only the number and percentage of subjects with progression or death will be provided.

Progression-Free Survival (PFS) is defined as the time that the subject is still alive after the original ablation procedure and with no evidence of any tumor progression (local, regional, or distant). The PFS rate will be estimated using the Kaplan-Meier (KM) method. The 95% CIs for median PFS and other quartiles will be estimated using the Brookmeyer-Crowley method. The PFS rates at 3, 6, 9, and 12 months will be estimated by the Kaplan-Meier method and their corresponding 95% CIs will be calculated using Greenwood's formula for estimating the variance and log-log transformation with back transformation to CIs on the untransformed scale. The censoring rule is described as below and frequency of subjects (n, %) experiencing PFS events and censored by reason will be provided.

For subjects who are alive and without tumor progression (locally, regionally, distantly) during the study follow-up period, the subject will be censored at the date of the last tumor assessment.

Listings will be provided.

#### **8.10.6 Overall Survival**

Analyses will be performed on the FAS and at subject level. On run-in set, only the number and percentage of subjects who have died will be provided.

Overall Survival (OS) is defined as the time that the subject is still alive after the original ablation procedure within the study duration. The OS rates will be estimated using the Kaplan-Meier method. The 95% CIs for median OS and other quartiles will be estimated using the Brookmeyer-Crowley method. The OS rates at 1, 3, 6, 9 and 12 months will be estimated by Kaplan-Meier method and their corresponding 95% CI will be calculated using Greenwood's formula for estimating the variance and log-log transformation. The censoring rule is described as below and frequency of subjects (n, %) experiencing death events and censored by reason will be provided.

For each subject who is not known to have died during the study follow-up period, the subject will be censored at last contact date (e.g., last contact date of AE end date, lesion assessment date, visit date, study completion date, or last known alive date).

### **8.10.7 Safety Analyses**

Analyses will be performed at subject level on the SAF. The AE summary will be provided on the FAS and run-in set as well.

All AEs that occur on or post the initial ablation date or occurs before the initial ablation date and related (Unlikely, Possibly, Probably, or Causal) to the study device or study procedure will be presented.

AEs will be coded using MedDRA. The number of events and the number and percentage of subjects reporting AEs and SAEs will be summarized at the MedDRA system organ class and preferred term level. The severity of AEs and SAEs will be summarized. The AEs and SAEs will also be summarized according to the Society of Interventional Radiology (SIR) classification. Similar summaries will also be provided for AEs and SAEs related to the study device, AEs and SAEs related to the study procedure, and device deficiencies. Related events are those where the relationship is indicated as Unlikely, Possibly, Probably, or Causal by the PI. In addition, related events where the relationship is indicated as Possibly, Probably, or Causal will also be summarized. Summaries of all AEs and SAEs reported within the first 30 days after the initial ablation procedure and overall will be generated. The incidence of predefined AEs will also be summarized and reported, including pneumothorax (all and those requiring chest tube drainage), hemorrhage (all and those requiring treatment), post-ablation syndrome, chest wall pain, pleural effusion (all the those requiring chest tube drainage), pneumonia, pulmonary or pleural abscess, other infections, and bronchopleural fistula.

All AE/device deficiencies will be listed.

All abnormal laboratory tests and positive blood or urine pregnancy test results will be listed.

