7.1.8. Safety Evaluation Method

1) Description of safety parameters

Safety parameters include:

- All AEs from the start of any ablation procedure (from the probe puncture on skin) to 30 days post-ablation or early discontinuation.
- All SAEs from the start of ablation procedure through the end of the study or early discontinuation.
- All device-related AEs, procedure-related AEs, device-related SAEs and procedure-related SAEs from the start of ablation procedure through the end of the study or early discontinuation.

The incidence of the prespecified AEs below will also be summarized and reported:

1. Pneumothorax (all and those requiring chest tube drainage)
2. Hemorrhage (all and those requiring treatment)
3. Post-ablation syndrome
4. Chest wall pain
5. Pleural effusion (all and those requiring chest tube drainage)
6. Pneumonia
7. Lung or chest abscess
8. Other infections
9. Bronchopleural fistula

2) Selection of method and time to evaluate, record, and analyze the safety parameters

From the time of signing the informed consent form until approximately 30 days (Visit 3) after ablation (including primary and repeat ablation) or early discontinuation, all adverse events will be recorded. During this period, all adverse events from the start of ablation (i.e., probe puncture on the skin) will be reported.

After approximately 30 days (Visit 3) post ablation, adverse events considered by the investigator as related to the study device or/and study procedures and all serious adverse events will be recorded and reported till the end of the study or early discontinuation.

For subjects who stop ablation and withdraw from the study without ablation power emission while the needle has punctured the skin during the ablation procedure, the subject will be followed up for safety events up to 30 days after the procedure. If the discontinued subject reports a serious adverse event, the subject will be followed until event resolution, stabilization, or until the event is adequately explained.

The safety parameters will be recorded on the e-CRF according to the investigator's record, medical record, and all other related source documents collected at each follow-up visit.

See Section 8 for safety endpoint analysis methods.

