 - Minimally include: “Chest CT + head MRI or CT + neck and supraclavicular lymph node ultrasound or CT + upper abdominal ultrasound or CT + bone scan” as recommended by the 2019 edition

of Chinese Medical Association Guidelines for Clinical Diagnosis and Treatment of Lung Cancer;

- Acceptable if available by SOC: “PET/CT from skull base to mid-thigh”;
- Nice to have if available by SOC: “Mediastinal staging”.
- o The images requirements for oligometastatic lung tumor diagnosis are:
 - Minimally cover the primary lesion, abdomen and chest;
 - Nice to have if available by SOC: brain MRI or CT if the investigator considers the patient having suspected brain metastases.
- The determination of whether the lung tumor to be ablated is GGO will be made by the investigator and classified as: pure GGO, partial solid GGO, and pure solid tumor.
- Quality of Life assessment: including EORTC QLQ-C30 and lung-specific QLQ-LC13.
- All relevant prior medications taken within 30 days of visit 1 will be recorded, including blood-thinning/anticoagulants, chemotherapy/targeted therapy/immunotherapy and other anti-neoplastic agents, steroids, anti-inflammatory drugs, NSAIDs, antibiotics, and drugs used to treat relevant medical history.
- For all anti-tumor agents used prior to ablation, the pre-ablation withdrawal time should also be recorded.
- The name, time, location and purpose of all concomitant procedures within 30 days before visit 1 (including but not limited to puncture, radiotherapy, ablation therapy, surgical resection, etc.) will be recorded.
- Review inclusion/exclusion criteria and determine whether the patient meets the participation criteria.
- Record AEs and SAEs from signing the ICF.

Pre-Ablation Screening

Subjects will be consented prior to any actual study-specific screening procedures being conducted. Subjects will be considered enrolled into the study upon satisfaction of the following criteria:

- Completion of the informed consent process and signing the Informed Consent Form (ICF).
- Verification of the eligibility criteria by the Principal Investigator (PI) and/or authorized investigators. The verification must be conducted by the PI and/or authorized investigators prior to performing any study-related procedure or completing any form associated with this study.

Pre-Ablation Screening Failures

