#### **1.3.2 Secondary Endpoints**

- Secondary Efficacy Endpoints

- Technical Success Rate: Percentage of tumors that achieve A0 or A1 ablation classification determinations (i.e., complete tumor ablation with a surrounding margin) based on the lung CT immediately following the initial ablation procedure.
- A0 Ablation Rate: Percentage of tumors that achieve A0 ablation (i.e., the ablation zone covers the tumor completely and has a minimal margin of at least 5mm for secondary lung tumors and at least 10mm for primary lung tumors) based on the lung CT immediately following the initial ablation procedure.

Note: NSCLC are primary tumors and oligometastatic lung tumors are secondary.

- Re-Ablation Technical Success Rate: Percentage of tumors that achieve Technical Success in the lung CT immediately following the repeat ablation with the study device during the study.
- Local Tumor Progression: Local tumor progression and time to local tumor progression of any original-ablated tumor(s).
- Progression-Free Survival: Length of the time the subject is still alive after the original ablation procedure and with no evidence of any tumor progression (local, regional, or distant).
- Overall Survival: Length of time that the subject is still alive after the original ablation procedure within the study duration.
- Safety Endpoints
  - All AEs from the start of any ablation procedure (starting from the time of probe puncture on skin) to 30 days post-ablation or early discontinuation.
  - All SAEs from the start of ablation procedure through the end of the study or early discontinuation.
  - All device-related AEs, procedure-related AEs, device-related SAEs, and procedure-related SAEs from the start of ablation procedure through the end of the study or early discontinuation.

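### SAP 8.10.7 lets adverse events that began before the ablation date into the safety tables, although the SAP's own safety endpoints start at the ablation procedure

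*SAP*

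**What the plan says.** SAP 1.3.2 gives the all-AE endpoint as "All AEs from the start of any ablation procedure (starting from the time of probe puncture on skin) to 30 days post-ablation" or early discontinuation. The SAE endpoint and the device- and procedure-related endpoints run from the start of the ablation procedure to the end of the study. None starts earlier.

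SAP 8.10.7 decides which events go into the tables. It takes all AEs on or after the initial ablation date and adds an AE that "occurs before the initial ablation date and related (Unlikely, Possibly, Probably, or Causal) to the study device or study procedure will be presented". Three further rules in that section matter here:

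- Main related-event tables: "Related events are those where the relationship is indicated as Unlikely, Possibly, Probably, or Causal by the PI".
- A second, narrower version: "In addition, related events where the relationship is indicated as Possibly, Probably, or Causal will also be summarized".
- Time windows: "Summaries of all AEs and SAEs reported within the first 30 days after the initial ablation procedure and overall will be generated".

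No onset limit is stated for the related-event tables or for the predefined AEs.

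The protocol separates recording from reporting. At Visit 1 (section 7.2.3) sites are told to "Record AEs and SAEs from signing the ICF". On reporting up to about 30 days after ablation, section 7.1.8 says: "During this period, all adverse events from the start of ablation (i.e., probe puncture on the skin) will be reported".

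**The concern.** Before the initial ablation date the study device has not been used. The added clause in 8.10.7 can therefore bring in only events of the screening period, or events with a doubtful rating. None of them belongs to an endpoint in 1.3.2.

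The SAP says that it overrides the protocol's statistical section where the two differ. That does not settle a conflict between two sections of the SAP. One programmer working from 1.3.2 and another working from 8.10.7 could produce different overall, procedure-related and pneumothorax incidences from the same data.

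Pneumothorax and hemorrhage are on the predefined list, and a needle biopsy can cause both. NSCLC must be biopsy-proven before ablation, while oligometastatic tumors may be diagnosed clinically. The 75% cap on either disease type allows 30 to 90 NSCLC subjects among the 120, so any such mixing would also vary with the disease mix.

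**Working it through.** The plan states no figure on this point, so the check is mainly a comparison of text.

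**1. Are pre-ablation events in the database?** Yes, if they occur after consent (protocol 7.2.3, Visit 1). The schedule of activities places biopsy at Visit 1, and its notes require the result before ablation. A biopsy done before consent produces no recorded AE.

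**2. What must happen for such an event to be tabulated?** The investigator must rate it at least Unlikely to the device or to the study procedure.

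- Device: the guide in protocol 14.1 lists the absence of a temporal relationship as a ground for Not Related. A rating of Not Related is natural for a device not yet used.
- Procedure: SAP 8.10.7 does not define the study procedure. Protocol 8.1 and 14.5 speak of the ablation procedure when they discuss relatedness, and the Visit 1 text in 7.2.3 uses the term for the ablation. Protocol 7.1.8, however, uses the plural, study procedures, which could be read to cover the Visit 1 biopsy.
- Guide wording: in 14.1, Unlikely covers events reasonably explained by another cause, and cases that cannot be assessed are to be classed as Possible.

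**3. Where does the event land?** Take an NSCLC subject with a biopsy after consent and a pneumothorax needing a chest tube on day -10, later ablated. Suppose it is rated Not Related to the device.

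| Rating to study procedure | Endpoint window (1.3.2) | Overall AE table | Procedure-related, main | Procedure-related, narrower | Predefined pneumothorax | 30-day table |
|---|---|---|---|---|---|---|
| Not Related | out | out | out | out | out | out |
| Unlikely | out | in | in | out | in | out |
| Possible or higher | out | in | in | in | in | out |

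The endpoint column is out in every row. Under 8.10.7 the same event is counted in three or four tables once the rating is Unlikely or higher.

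**4. Size per subject.** Safety is analyzed on the SAF, which includes two run-in subjects per site. The number of sites is not given, so 4 to 15 is an assumption.

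- SAF = 120 + 2 × sites
- 4 sites: 120 + 8 = 128, and 1/128 = 0.78 points per subject
- 15 sites: 120 + 30 = 150, and 1/150 = 0.67 points per subject
- Five such subjects: 5/128 = 3.9 points; 5/150 = 3.3 points

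This assumes that enrollment is not increased above 120 and ignores subjects replaced after puncture, who also count in the SAF. The figure applies to a subject who is in the table only because of the pre-ablation event. Someone with the same event after ablation is counted once either way.

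**The case against.** The strongest reply is that the rule does little in practice. An event enters only through the investigator's rating, and the protocol's guide points to Not Related where there is no temporal link. If the study procedure means the ablation, a biopsy complication should be rated Not Related to it as well. The narrower summary removes Unlikely events from the related tables, and all AEs are listed, so early events can be traced. Protocol 3.2 describes the safety result for the registration submission as that within 30 days after ablation, and the 30-day table excludes pre-ablation events. Safety has no hypothesis test or success criterion, and any error works against the sponsor.

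All of this stands as a limit on the consequence. It does not remove the conflict. The meaning of study procedure is left to the reader, the narrower summary covers only the related tables, and the overall and predefined tables have no other protection.

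A reader might also infer three stronger points that the documents do not support:

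- **That screening complications automatically inflate the device-related rate.** They do not. The device and procedure ratings are separate, and Not Related is the natural device rating before any use.
- **That counting from the calendar day of ablation, not from puncture, is itself an error.** Protocol 14.5 reports AEs from Visit 2A, the day of ablation, so 8.10.7 has support there.
- **That the inflation can be put in figures.** The share of subjects biopsied after consent, the complication rate and the rating pattern are not given, and the share could be zero.

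**Conclusion.** The conflict is real and lies within the SAP. Followed literally, 8.10.7 allows events from before any device use to count in the overall, procedure-related and predefined AE incidences, while 1.3.2 excludes them from every safety endpoint. Entry into the device-related table is possible but less likely.

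The total size cannot be derived. Per affected subject it is about 0.7 to 0.8 points, on the assumption of 4 to 15 sites and 120 non-run-in subjects. The direction is upward. The primary effectiveness conclusion and the 30-day AE summary are unaffected. The point is worth correcting because the descriptive rates should match their own definition, not because it threatens the trial's result.

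**What to change.** Make three changes in SAP 8.10.7:

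1. Limit the overall, device-related, procedure-related and predefined AE incidence tables to AEs with onset on or after the initial ablation date. Where onset time is available, use onset at or after probe puncture. Count ablation-day events without a time.
2. Show AEs with onset between consent and ablation in a separate count and listing, whatever their rating.
3. Define the study procedure, for the relatedness tables, as the ablation procedure, in line with protocol 8.1 and 14.5.

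The cost is short SAP wording, one extra table or listing, and a flag in the AE dataset. Onset time is not essential, because ablation-day events without a time stay in the tables. Nothing is hidden, since the earlier events remain visible in their own display.

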## **8.11 Exploratory Endpoints and associated hypotheses**

No hypothesis testing is performed for the exploratory endpoints. Exploratory endpoints will be analyzed on the FAS and run-in set.

### **8.11.1 Ablation-Procedure Related Pain**

Descriptive summary statistics of actual values and change from pre-ablation by post-ablation analysis time point (i.e., visit 2B, visit 3-6) will be presented by ablation-procedure related pain measured by Numeric Pain Rating Scale. The change from baseline will be tested by paired-t test. The number of missing, mean, SE, and 95% CI based on student's t distribution will be provided.

The shifting table of baseline vs. post-baseline will be presented. 0: No pain; 1-3: Mild pain; 4-6: Moderate pain; 7-10: Severe pain. The number of subjects and percentage will be provided.

## 8.11.2 Quality of life

The quality of life assessment included the EORTC QLQ-C30 (version 3.0) and the lung-specific EORTC QLQ-LC13 (Figure1 and Figure2). The EORTC QLQ-C30 is scored for global health status/QOL and 5 functional (physical, role, emotional, cognitive, and social) and 3 symptom (fatigue, nausea and vomiting, and pain) scales. Additionally, 6 single-item scales are included (dyspnea, appetite loss, constipation, diarrhea, and financial difficulties). The EORTC QLQ-LC13 module incorporates 1 multi-item scale to assess dyspnea and a series of single-item scales assessing coughing, pain, sore mouth, dysphagia, peripheral neuropathy, alopecia, and hemoptysis. For both the EORTC QLQ-C30 and QLQ-LC13, raw scores are converted into scale scores ranging from 0 to 100. For the GHS/QOL and functional scales, higher scores represent better HRQOL; for the symptom scales, lower scores represent fewer symptoms. Descriptive statistics of all scale scores over time and change from pre-ablation will be provided for EORTC QLQ-C30 and QLQ-LC13, respectively.

The change from baseline to each post-ablation visit will be tested by paired-t test. The number of missing, mean, standard error (SE), and 95% CI based on student's t distribution will be provided.

Figure1 Scoring the QLQ-C30 version 3.0

	Scale	Number of items	Item range*	Version 3.0 Item numbers	Function scales
Global health status / QoL					
Global health status/QoL (revised) †	QL2	2	6	29, 30	
Functional scales					
Physical functioning (revised) †	PF2	5	3	1 to 5	F
Role functioning (revised) †	RF2	2	3	6, 7	F
Emotional functioning	EF	4	3	21 to 24	F
Cognitive functioning	CF	2	3	20, 25	F
Social functioning	SF	2	3	26, 27	F
Symptom scales / items					
Fatigue	FA	3	3	10, 12, 18	
Nausea and vomiting	NV	2	3	14, 15	
Pain	PA	2	3	9, 19	
Dyspnoea	DY	1	3	8	
Insomnia	SL	1	3	11	
Appetite loss	AP	1	3	13	
Constipation	CO	1	3	16	
Diarrhoea	DI	1	3	17	
Financial difficulties	FI	1	3	28	

\* Item range is the difference between the possible maximum and the minimum response to individual items; most items take values from 1 to 4, giving range = 3.

† (revised) scales are those that have been changed since version 1.0, and their short names are indicated in this manual by a suffix "2" – for example, PF2.

Figure2 Scoring the QLQ-LC13

#### Scoring of the lung cancer module

The lung cancer module incorporates one multi-item scale to assess dyspnoea, and a series of single items assessing pain, coughing, sore mouth, dysphagia, peripheral neuropathy, alopecia, and haemoptysis.

The scoring approach for the QLQ-LC13 is identical in principle to that for the symptom scales / single items of the QLQ-C30.

Scale name	Scale	Number of items	Item range*	QLQ-LC13 Item numbers	†
Symptom scales / items					
Dyspnoea †	LCDY	3 †	3	3,4,5	X
Coughing	LCCO	1	3	1	
Haemoptysis	LCHA	1	3	2	
Sore mouth	LCSM	1	3	6	
Dysphagia	LCDS	1	3	7	
Peripheral neuropathy	LCPN	1	3	8	
Alopecia	LCHR	1	3	9	
Pain in chest	LCPC	1	3	10	
Pain in arm or shoulder	LCPA	1	3	11	
Pain in other parts	LCPO	1	3	12	

\* “Item range” is the difference between the possible maximum and the minimum response to individual items.

† The dyspnoea scale should only be used if all three items have been answered. Some respondents ignore question 5 because they never climb stairs; in this case, the score for the dyspnoea scale would be biased if it were based upon the other two items. Hence if item 5 is missing then items 3 and 4 should be used as single-item measures.

### 8.11.3 ECOG performance status

Descriptive summary statistics of actual values and shift from pre-ablation by post-ablation analysis time point (i.e., visit 2B, visit 3-6) will be presented by ECOG performance status score. Number of subjects and percentage will be provided.

### 8.11.4 Ablation procedure related indicators

The following analyses will be performed on the tumor level:

Selected information from the ablation procedure (number of ablation cycles, duration of ablation for each cycle, total duration of ablation, maximum power applied, maximum temperature observed, and number and types of probes used) will be summarized for the initial ablation and re-ablations, respectively, with descriptive statistics.

The following analyses will be performed on the subject level:

Duration of procedure, mode of anesthesia, and guidance method used will be summarized for the initial ablation and re-ablations, respectively, with descriptive statistics.

Listings will be provided.

